3. PATIENT SELECTION – ELIGIBILITY

3.1 Inclusion Criteria

- 3.1.1 Males age 18 and over
- 3.1.2 Histologically confirmed prostate cancer that has recurred following primary definitive treatment of localized prostate cancer (either surgery, radiotherapy or both)
 - PSA biochemical recurrence defined as either:
 - PSA \geq 0.2 ng/dL following radical prostatectomy
 - PSA increase \geq 2 ng/mL above PSA nadir value following radiotherapy of primary tumor
- 3.1.3 Five or fewer synchronous metastatic lesions (on imaging) with no evidence of residual local disease
- 3.1.4 ECOG performance status 0 – 2 (see **Appendix A**)
- 3.1.5 Approval by screening eye exam (disqualifying baseline conditions listed in 3.2.2, below)
- 3.1.6 Ability to provide informed consent

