5.5 Duration of Therapy

In the absence of treatment delays due to adverse event(s), hydroxychloroquine treatment will continue for 3 months or until one of the following criteria applies:

- Disease Progression, assessed by standard of care and defined as either:
 - PSA progression (an increase in PSA > 25% above baseline at study entry), or
 - Symptomatic progression (increasing pain from metastatic lesion), or
 - Progression of baseline-detected lesions (soft-tissue lesions as assessed by RECIST and bone lesions as assessed by the MDA criteria (respectively, Appendix H.1 and Appendix H.2)).
Additionally, CT C/A/P and/or fluciclovine or PSMA PET scans may be performed at the time of either Symptomatic or PSA Progression at discretion of the treating physician.
 - Appearance of new metastatic lesions
- Intercurrent illness that prevents further administration of treatment
- Unacceptable adverse event(s)
- Patient decides to withdraw from the study
- General or specific changes in the patient's condition that render the patient unacceptable for further treatment in the judgment of the investigator

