Baseline evaluations are to be conducted within 8 weeks prior to start of HCQ. Scans and ophthalmologic exam must be completed less than 8 weeks prior to the start of HCQ regimen. In the event the patient's condition is deteriorating, laboratory evaluations should be repeated more frequently, as clinically indicated and at the discretion of the treating physician. At PSA progression or symptomatic progression: PSA, history and physical/toxicity assessment, CT C/A/P and/or fluciclovine or PSMA PET scans to be performed at discretion of treating physician, per standard of care.

Study Calendar											
Procedures	Pre-study Screening	Enrollment/Baseline Visit 1, Day 0	Day 14 post-HCQ initiation	Day 30 post-HCQ initiation	Day 60 post-HCQ initiation	90 days post-HCQ initiation	6-months post-HCQ cessation	1 Year Post- HCQ cessation	2 Years Post-HCQ cessation	3 Years Post-HCQ cessation	Off-Study
HCQ Drug Dispensing		R		R	R	R					
Adverse Event Evaluation		R	R	R	R	R					
HCQ compliance (pill diary)				R	R	R					
PAR-4 blood sample ¹		R	R	R	R	R	R	R			
PBMCs blood collection ²		R		R	R						
Quality of Life ³		R				R	R	R			
Informed Consent	R										
Demographics	R										
Ophthalmologic Exam ⁴	R	← ----- S ** ----- →									
PSA (serum, one tube) ⁵	S	R		R		S	S	S			
Imaging ⁶											
Fluciclovine or PSMA PET or PET/CT scan ^{6a}	S**										
Bone scan ^{6a}	S**										
CT chest, abdomen, pelvis ^{6a}	S**										
MRI of pelvis ^{6b}	S *										
Assessment of Disease Progression ^{6c}							S * , **				
CBC w/ differential	S	*	*	S	S	S	**	**			
CMP **	S	*	*	S	S	S	**	**			
Concomitant Medications ⁷	S	S	S	S	S	S					
Medical History	S										
Height ⁸		S									
Physical Exam with vitals (including weight) and ECOG Performance status	S	**	S**	S	S	S	**	**			
Survival Status									R	R	R
Record date of ADT initiation ⁹											

Study Calendar											
Procedures	Pre-study Screening	Enrollment/Baseline Visit 1, Day 0	Day 14 post-HCQ initiation	Day 30 post-HCQ initiation	Day 60 post-HCQ initiation	90 days post-HCQ initiation	6-months post-HCQ cessation	1 Year Post- HCQ cessation	2 Years Post-HCQ cessation	3 Years Post-HCQ cessation	Off-Study

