
NOTES: * per standard of care ** at the discretion of the treating physician.
 
Legend: S = standard of care; R = research; PSA, prostate-specific antigen; PET, positron emission tomography scan; HCQ, hydroxychloroquine; PAR-4, prostate apoptosis response-4; PSMA, prostate-specific membrane antigen PET scan
 
1: Blood (1 tube) will be drawn at each of the 7 noted timepoints for PSA and PAR-4 levels; plasma is preferred (serum is acceptable). Timepoints may be +/- 72-hour window at Pre-study and Enrollment. For Day 14, Timepoints may be +/- 120-hour window. Timepoints may be +/- 28-day window at the 3-, 6- and 12-month f/u, coinciding with a clinic visit.
 
2: for collection of PBMCs (peripheral blood mononuclear cells): one tube per collection timepoint, slated for Day 0, Day 30 and Day 60. Day 0 and Day 30 timepoints have a +/- 14-day window. Day 60 has a +6 week window. This is explicated in greater detail in study lab manual.
 
3: QOL is assessed via EORTC QLQ-C30 + QLQ-PR25 at 4 timepoints 
 - at a clinic visit prior to initiation of HCQ - at a clinic visit; either the end of HCQ administration OR when HCQ is discontinued (if stop it early) - at 6-mos and 12-mos post-treatment. These final two QOL timepoints can be +/- 8 weeks, and conducted during a regularly scheduled, standard of care clinic visit. 
 
4: Requisite pre-study eye exam; Eye exam may be repeated during HCQ administration if vision complaints.
 
5: One tube of blood will be drawn at each of the 6 noted timepoints for serum PSA; this is standard of care for baseline and every 3 months (4 of the 6 draws), with two additional draws scheduled. Timepoints may be +/- 72-hour window at screening and enrollment.
 
6: Imaging at baseline, pre-study: Patients who have confirmed recurrent disease of the prostate are deemed ineligible for this trial. As such, all eligible patients will undergo standard of care imaging to identify metastases (initial evaluation of status/extent of recurrent disease), including: 6a: All eligible patients will undergo standard of care imaging to assess extent of metastatic disease at baseline; fluciclovine or PSMA PET scans are preferred; other scans (PET/CT scan, bone scan and/or CT of the chest, abdomen and pelvis) may be performed as needed at baseline to assess extent of metastatic disease, per standard of care. 6b: Additionally, eligible patients who have undergone radiation prior to study enrollment will have an MRI of pelvis (in addition to previously named imaging studies) to assess for recurrent local disease. Suspicious lesions of the prostate seen on MRI will be biopsied. 6c: Imaging on Study as work-up for disease progression: Once a patient is enrolled on-study, imaging to assess disease progression will proceed per standard of care, based on clinical indicators such as rising PSA and/or other clinical symptoms. Per RECIST 1.1, tumor re-evaluation scheduled every 6-8 weeks at the discretion of the treating physician based on clinical indicators. Notably, a rising PSA and/or other clinical symptoms could trigger a scan/imaging in an earlier timeframe.
 
7: Concomitant Medications will be assessed per standard of care at the discretion of the treating physician; during HCQ administration, Con Meds will be assessed with a particular focus on medications contraindicated for use with HCQ.
 
8: Height will be evaluated once while on-study. Height can either be assessed via the patient's medical record, and/or assessed directly (in conjunction with vital signs during a clinic visit)
 
9: ADT initiation: record date and reason for ADT initiation. Reasons for ADT initiation include: PSA/biochemical progression, Symptomatic Progression, Local Progression of baseline-detected lesions (either soft-tissue or bone lesions), or Appearance of new metastatic lesions.
											

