
11. MEASUREMENT OF HCQ EFFECT

11.1 PRIMARY OBJECTIVE

To assess the effect of HCQ on PAR-4, first compliance with HCQ planned dose regimen should be ascertained.

HCQ regimen compliance: pill diaries (Appendix D) and/or patient-reported HCQ compliance will be evaluated to assess participant adherence to HCQ daily regimen at follow-up clinic visits with study staff. Additionally, study staff may institute a telephone check with study participants on a PRN basis, should compliance to the HCQ regimen need to be monitored outside regular clinic visit schedule.

Participants who completed 80% of the planned HCQ doses will be considered evaluable for the Primary Endpoint, PAR-4 increase.

PAR-4 level will be assessed for each participant at the following timepoints:

- Enrollment/Baseline visit
- Day 14 post- HCQ initiation
- Day 30 of HCQ
- Day 60 of HCQ
- Day 90 of HCQ
- 6-month follow-up (during a standard of care visit)
- 12-month follow-up (during a standard of care visit)

It is expected that HCQ will induce an elevation of PAR-4 expression among 50% of the participants within the 90-day administration of HCQ. The elevation is expected to be a 50% increase from baseline PAR-4 levels among half of the study participants.

11.2 SECONDARY OBJECTIVES:

11.2.1 HCQ safety analysis and Treatment Toxicity: frequency and incidence tables of toxicity and AEs will be generated. Toxicity will be assessed using Common Terminology Criteria for Adverse Events V5.0 (for HCQ and for radiation therapy), as well as the Clavien-Dindo classification of surgical complications in the case of patients who underwent surgery (Appendix F). All patients will be evaluable for toxicity (HCQ) from the time of their first treatment with Hydroxychloroquine.

11.2.2 HCQ immunologic effect on PAR-4 Levels: as measured by serum (or plasma) blood collected at multiple timepoints. PAR-4 secretion is expected to come primarily from normal cells of the patient. The contribution of the tumor cells to serum levels of PAR-4 is expected to be minimal, but this has not been directly tested. Association between PAR-4 levels and clinical stage will be assessed.

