11.3 Four Types of Disease Progression

1. **PSA or Biochemical Progression:** defined as a PSA increase of $\geq 25\%$ and ≥ 2 ng/mL if PSA was ≥ 2 ng/mL from baseline (OR a PSA increase of $\geq 25\%$ if PSA was < 2 ng/mL at study enrollment).
2. **Symptomatic Progression:** defined as increasing pain from baseline-detected metastatic lesion. Time to first symptomatic event will be calculated from study enrollment until the event of symptoms due to metastatic disease.
3. **Local Progression of baseline-detected lesions depend on site:**
 - 3a. ***soft-tissue metastatic lesion:*** local progression is defined as an increase of $\geq 20\%$ in the largest tumor dimension with a minimum absolute increase of 5 mm. All lesions are considered target lesions, irrespective of size, if they are suspicious on choline PET-CT. See Appendix H.1 for RECIST v1.1.
 - 3b. ***bone metastases:*** local progression is assessed using the MD Anderson Cancer Center-criteria²⁶⁻²⁷, and defined as a $\geq 25\%$ increase in size of a measurable lesion or a $\geq 25\%$ increase in the size of ill-defined lesions on CT considered to be progression. MDA bone-specific response criteria in Appendix H.2.
4. **Distant Progression:** appearance of new metastatic lesions

11.4 Definition of Disease Assessments to evaluate Progression-Free Survival and ADT-Free Survival

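### Section 5.5 stops HCQ for PSA progression at any rise above 25%, while Section 11.3 also requires at least 2 ng/mL, so the rules disagree for entry PSA from 2 to just under 8 ng/mL

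*Combined protocol and SAP*

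**What the plan says.** Section 5.5 (Duration of Therapy) continues HCQ for 3 months unless a listed criterion is met. Disease progression is the first criterion, and its first form is "PSA progression (an increase in PSA > 25% above baseline at study entry". No absolute rise is required. Investigator judgment is a separate item in the same list.

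Section 11.3 defines PSA or biochemical progression in two parts. The first is a rise of at least 25% and at least 2 "ng/mL if PSA was ≥ 2 ng/mL from baseline". The second is a rise of at least 25% alone "if PSA was < 2 ng/mL at study enrollment". Section 11.4.2 takes its PFS events from the four types in 11.3.

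Section 11.1 links dosing to the primary analysis: "Participants who completed 80% of the planned HCQ doses will be considered evaluable for the Primary Endpoint, PAR-4 increase". Section 13.3 repeats the 80% requirement.

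In the Section 10 calendar, the PSA row has draws at screening, "Enrollment/Baseline Visit 1, Day 0", Day 30, Day 90, 6 months and 1 year. Footnote 5 agrees: "One tube of blood will be drawn at each of the 6 noted timepoints for serum PSA". Footnote 1 differs: "Blood (1 tube) will be drawn at each of the 7 noted timepoints for PSA and PAR-4 levels". Those seven are the PAR-4 timepoints, which include Days 14 and 60. Footnote 1 also gives the 3-month draw a window of plus or minus 28 days.

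**The concern.** Sections 5.5 and 11.3 list the same four kinds of progression (PSA, symptomatic, baseline lesions, new lesions), and both use the Appendix H criteria for lesions. Only the PSA criterion has a different threshold. Nothing in 5.5 refers to 11.3, gives a reason for the difference, or presents the rule as a separate, more sensitive stop.

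A man can therefore be taken off study drug for PSA progression when the protocol's own definition says he has not progressed. If this happens early, the 80% rule also removes him from the primary PAR-4 analysis. The trial enrols 20 to obtain 18 evaluable men, so an exclusion caused only by inconsistent wording is worth preventing.

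**Working it through.** **The plan's own figure.** Section 13.1.2 states 84% power for 18 men, 0.50 against 0.20, two-sided 5%. The normal approximation gives Φ[(0.30 − 1.96·√(0.2·0.8/18)) / √(0.5·0.5/18)] = 83.6%, which agrees. With 10% dropout, 18/0.9 = 20. The point below does not depend on these figures and does not change them.

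**Step 1: thresholds.** Let b be PSA at study entry, in ng/mL.
- Section 5.5 stops HCQ when PSA exceeds 1.25b.
- Section 11.3 calls progression when PSA reaches 1.25b if b < 2, or the larger of 1.25b and b + 2 if b ≥ 2.

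The rules differ when b ≥ 2 and 0.25b < 2, that is, for 2 ≤ b < 8.

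| Entry PSA | 5.5 stops HCQ above | 11.3 progression at | Rise needed under 11.3 |
|---|---|---|---|
| 1.9 | 2.375 | 2.375 | 25% |
| 2 | 2.5 | 4.0 | 100% |
| 4 | 5.0 | 6.0 | 50% |
| 6 | 7.5 | 8.0 | 33% |
| 7.9 | 9.875 | 9.9 | 25.3% |
| 8 | 10.0 | 10.0 | 25% |

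Example: 4.0 to 5.2 is a rise of 30% and 1.2 ng/mL. It stops HCQ under 5.5 and is not progression under 11.3. Below 2 and from 8 upward, the only difference is > against ≥ at exactly 25%.

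**Step 2: can a man enter in this range?** Yes. After radiotherapy, Section 3.1.2 requires a rise of at least 2 "ng/mL above PSA nadir value following radiotherapy of primary tumor", so his PSA has reached at least 2. No upper limit is set. The documents give no distribution of entry PSA.

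**Step 3: when could the rule act, and what dose would have been taken?** Two tablets a day for 90 days is 180 doses, and 80% of that is 144 doses, or Day 72 with none missed.
- Day 30, the only draw in the PSA row between Day 0 and the 3-month visit: 60/180 = 33%. Not evaluable.
- 3-month draw: with the footnote 1 window it may fall from Day 90 − 28 = 62. At Day 62 the fraction is 124/180 = 69%, which fails. From about Day 72 it passes.
- Days 14 and 60, only if footnote 1 is right against the PSA row and footnote 5: 28/180 = 16% and 120/180 = 67%. Both fail.

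**Step 4: PFS.** The first PSA item in 11.4.2 repeats only the part for entry PSA of 2 or more. The section opens by pointing to the 11.3 definitions and applies all of them. The restatement is incomplete, but the event definition is intact.

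**The case against.** The best defence is that a stopping rule need not match an endpoint definition. Each section can be applied as written, and a sensitive stop for an investigational add-on is a legitimate choice. Under 11.3, a man entering at PSA 2 would need his PSA to double before it stopped HCQ. This stands as an argument for a deliberate stricter rule. It does not explain why the stricter rule carries the same label, with no stated intent, beside three other criteria that match 11.3.

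It also stands that few men may be affected. HCQ starts 2 weeks before surgery or radiation (Section 5.3), so lesion treatment begins around Day 14, before the Day 30 draw. Assume exponential growth from entry PSA 4.0. Uninterrupted growth to Day 30 puts the rules in conflict for doubling times of 30/log2(1.5) = 51 to 30/log2(1.25) = 93 days. If growth stops at Day 14, the range is 14/log2(1.5) = 24 to 14/log2(1.25) = 43 days. If PSA falls after treatment, fewer men still would be affected.

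Finally, it is the 80% rule that removes men from the analysis, and it does so for any early stop. Aligning the PSA definitions leaves that rule as it is.

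Three stronger readings are tempting, and the documents support none of them:
- **A reader might infer lost PFS events.** Section 11.4.2 adopts the 11.3 definitions, so none is lost.
- **A reader might infer a loss of power.** The number of men lost is unknown, and the cost per man is not fixed. At 18, 17 and 16 evaluable men, power is 83.6, 81.8 and 79.7% by the normal approximation, but 76.0, 68.5 and 77.3% by an exact two-sided test (minimum likelihood).
- **A reader might infer that any PSA stop before Day 90 makes a man non-evaluable.** The window on the 3-month draw allows a stop after Day 72.

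**Conclusion.** The inconsistency is real and minor. For entry PSA from 2 to just under 8 ng/mL, PSA progression has two thresholds, and the gap between them shrinks from 1.5 ng/mL at entry PSA 2 to zero at 8. The clear consequence is at the Day 30 draw: HCQ can stop at about 33% of planned doses, and the man leaves the primary PAR-4 analysis, for a rise that 11.3 does not call progression. A stop at the 3-month draw may or may not fail the 80% rule. Any effect at Days 14 and 60 depends on which calendar footnote is correct.

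The threshold result follows from the text alone. The dose fractions assume full adherence up to the stop and a stop on the day of the draw. How many men are affected depends on entry PSA and on PSA behaviour after lesion treatment. The documents give neither, and the number may be zero.

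**What to change.** In Section 5.5, replace the PSA criterion with *PSA progression as defined in Section 11.3* and keep the investigator-judgment stop. If a stricter stop is intended, say so in 5.5 and rename it, for example *PSA rise above 25%, HCQ discontinuation only*, so that it is not recorded as progression. The loss of evaluability would then remain as a deliberate choice.

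For consistency, the same amendment could restate both parts of the 11.3 definition in 11.4.2, name the Day 0 PSA as the reference value, and reconcile calendar footnotes 1 and 5 on the PSA draws.

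The cost is a short wording amendment, with no added visits, tests or patients. The clinical downside of adopting 11.3 is that some men with a rise above 25% but below 2 ng/mL, such as 2.0 to 3.9, stay on HCQ for the rest of the 90 days unless the investigator stops it. The change leaves the 80% rule as it is and does not help men entering below 2 or at 8 ng/mL and above.

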5.6 Duration of Follow-up

Patients will be followed for up to three years post-therapy or until death, whichever occurs first. Patients removed from study for unacceptable adverse event(s) will be followed until resolution or stabilization of the adverse event.

6. DOSING DELAYS AND DOSE MODIFICATIONS

Dose schedule and dose reduction schedule for hydroxychloroquine (HCQ):

Dose Level	HCQ Dose
1	200 mg, twice a day (total daily dose, 400 mg)
-1	200 mg, daily

If a participant is unable to tolerate 200 mg per day of HCQ, he will be removed from the study.

**6.1 HCQ Dose Modifications for Non-Hematologic Toxicities that are deemed
Possibly, Probably or Definitely related to Hydroxychloroquine**

Nausea and/or Vomiting	Management/Next Dose for Hydroxychloroquine
≤ Grade 1	No change in dose
Grade 2	Hold until ≤ Grade 1. Resume at same dose level.
Grade 3 or 4	Hold* until < Grade 2. Resume at one dose level lower, if indicated.
*Patients requiring a delay of >2 weeks should go off protocol therapy.	
Recommended management: Re-educate patient to take with meals and anti-emetics. Adjunct anti-nausea therapy is permitted and should be recorded when used.	

Diarrhea	Management/Next Dose for Hydroxychloroquine
≤ Grade 1	No change in dose
Grade 2	Hold until ≤ Grade 1. Resume at same dose level.
Grade 3 or 4	Hold* until < Grade 2. Resume at one dose level lower, if indicated.
*Patients requiring a delay of >2 weeks should go off protocol therapy.	
Recommended management: Loperamide antidiarrheal therapy Dosage schedule: 4 mg at first onset, followed by 2 mg with each loose bowel movement until diarrhea-free for 12 hours (maximum dosage: 16 mg/24 hours) Adjunct anti-diarrheal therapy is permitted and should be recorded when used.	

Visual Changes	Management/Next Dose for Hydroxychloroquine
≤ Grade 1	No change in dose
Grade 2 or greater	Permanently discontinue.
The methods recommended for early diagnosis of "chloroquine retinopathy" consist of (1) fundoscopic examination of macula for fine pigmentary disturbances or loss of foveal reflex & (2) examination of the central visual field with a small red test object for pericentral or paracentral scotoma or determination of retinal thresholds to red.	

Pustular or Bullous Dermatitis	Management/Next Dose for Hydroxychloroquine
≤ Grade 1	No change in dose
Grade 2	Hold until ≤ Grade 1. Resume at same dose level.
Grade 3 or 4	Hold* until < Grade 2. Resume at one dose level lower, if indicated.
*Patients requiring a delay of >2 weeks should go off protocol therapy.	

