11.4.1 ADT-Free Survival

Indications to start Androgen Deprivation Therapy include appearance of new metastases (i.e., progression to more than the three baseline-detected metastases, “distant progression”), or local progression of baseline-detected metastases.

ADT initiation can be considered at Symptomatic Progression or at PSA Progression. Additionally, CT C/A/P and/or fluciclovine or PSMA PET scans may be performed at the time of either Symptomatic or PSA Progression at discretion of the treating physician.

Date of ADT initiation will be recorded for each participant, accompanied by the reason for initiation.

ADT-free Survival is defined as the time between study enrollment until the start of ADT or death as a result of any cause. Patients who do not start ADT at the time of last follow-up will be censored at that time point.

- Initiation of ADT will be recorded if it occurs after initiation of HCQ. This will also be recorded for enrolled patients who have ADT initiation occurring after completion of surgery/radiation but prior to HCQ initiation (as this is exclusion criterion, the patient will be removed from the study).
- After HCQ administration is completed, survival status will be assessed at ongoing clinic visits for one year post-enrollment, and afterwards, annually for up to 2 additional years (i.e., at Year 2 post-enrollment and at Year 3 post-enrollment).

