11.4.2 Progression-Free Survival (time to clinical progression)

Four types of progression are defined in 11.3. Progression is calculated from time of study enrollment until progression (per the 4 specified definitions) or death. Events for PFS are:

1. PSA or biochemical progression: defined as a PSA increase of $\geq 25\%$ and ≥ 2 ng/mL (if PSA was ≥ 2 ng/mL from baseline)
2. Symptomatic progression: increasing pain from metastatic lesion
3. Local progression of baseline-detected lesions: each metastasis is a target lesion independently assessed as:
 - soft-tissue lesions assessed per RECIST v1.1 (Appendix H.1)
 - bone lesions assessed per MDA bone-specific response criteria (Appendix H.2)
4. Distant progression: appearance of new metastatic lesions.

If an event is identified, then the time to the event will be recorded as the first instance where any of the above four situations occur.

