13.3.2 Analysis of Secondary Endpoints

Clinical Endpoints.

Progression-free survival (PFS) will be estimated using the Kaplan-Meier method and estimates of median PFS and PFS rates at specific time points will be calculated.

Likewise, median, 1-year and 3-year ADT-free survival will be estimated using the Kaplan-Meier method.

Exploratory analysis for association of PFS and ADT-free survival with PAR-4 and PSA levels will be assessed using the Cox regression model.

Correlative and QOL endpoints. PSA levels will be assessed according to the schedule described by the study calendar above and PSA doubling time will be calculated. Association of PSA levels with PAR-4 levels will be determined using Spearman or Pearson’s correlation coefficient. Quality of life (QOL) measured by the EORTC QLQ-C30 supplemented with QLQ-PR25 will be evaluated and descriptive statistics of QOL scores will be calculated. Association of QOL with PAR-4, PSA and clinical endpoints will be determined in an exploratory manner using correlations and survival analysis models.

Safety analysis. All patients who received study drug will be included in the safety analysis. Frequency and incidence tables of toxicity and AEs will be generated in the overall patient group. We will generate a safety report for review by the Markey Cancer Center’s Data Safety and Monitoring Committee (DSMC) based on an intent-to-treat population.

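### Sections 6 and 5.6 can be read as ending progression and ADT follow-up for men who cannot tolerate HCQ, while other sections imply they stay in; the text needs reconciling

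*Combined protocol and SAP*

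**What the plan says.** On leaving treatment and leaving the study:

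- Section 6, below the dose-level table: "If a participant is unable to tolerate 200 mg per day of HCQ, he will be removed from the study".
- Section 6.1 and 6.2 tables, for a prolonged hold: "Patients requiring a delay of >2 weeks should go off protocol therapy". For visual changes of grade 2 or worse, 6.1 has HCQ stopped for good. Neither mentions removal from the study.
- Section 5.6 opens with a general rule: "Patients will be followed for up to three years post-therapy or until death, whichever occurs first". It then adds: "Patients removed from study for unacceptable adverse event(s) will be followed until resolution or stabilization of the adverse event".

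On the endpoints:

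- Section 11.4.1: "ADT-free Survival is defined as the time between study enrollment until the start of ADT or death as a result of any cause". Its censoring rule is: "Patients who do not start ADT at the time of last follow-up will be censored at that time point".
- Section 11.4.2: "Progression is calculated from time of study enrollment until progression (per the 4 specified definitions) or death". No censoring rule is given for PFS.
- Section 13.3.2: "Progression-free survival (PFS) will be estimated using the Kaplan-Meier method". ADT-free survival is handled the same way, with a median and 1-year and 3-year rates. Exploratory Cox models use the same two endpoints.

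**The concern.** Stopping a drug and ending outcome follow-up are different events, and the protocol does not keep them apart. Elsewhere it has wording for stopping HCQ alone, but for men who cannot tolerate the lowest dose level it uses removal from the study. Section 5.6 then ties follow-up after such a removal to the adverse event, not to progression, ADT start or death.

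HCQ is given for 90 days and the endpoints run to 3 years, so a removal of this kind falls very early. Kaplan-Meier treats a censored man as having the same future risk as those still under observation. Here the censoring is triggered by treatment toxicity. The plan neither argues that toxicity is unrelated to outcome nor offers a sensitivity analysis. At stake is whether PFS and ADT-free survival describe all enrolled men or mainly those who tolerated HCQ. Outcomes that were never collected may not be recoverable at analysis.

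**Working it through.** **Reading the passages together**

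| Place | Points to |
|---|---|
| Section 6, intolerance sentence | Leaves the study |
| 5.6, second sentence | Follow-up ends with the adverse event |
| 11.4.1, ADT started before HCQ | Removal from the study is used for a man who meets an exclusion criterion, so the phrase seems to mean leaving the trial |
| 5.6, first sentence | Up to 3 years for patients in general |
| 5.5 | An unacceptable adverse event ends HCQ treatment |
| Section 10 calendar | Later visits are timed from HCQ cessation; survival status is a research item in the off-study column |
| Section 10, note 3 | QoL when HCQ stops early, then at 6 and 12 months |
| 11.4.1, ADT date | Recorded for every participant |

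The first three rows point one way and the last five the other. No section says that progression or ADT start is still collected after removal for toxicity.

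**The plan's own figures.** The documents give no power or precision for PFS or ADT-free survival. Section 13.1.2 gives 84% power for the primary test with n = 18, 0.50 against 0.20, two-sided 5%. The normal approximation gives Φ[(0.30 × √18 − 1.96 × √(0.20 × 0.80)) / √(0.50 × 0.50)] = 83.6%, which agrees. Enrolment is 18 / 0.90 = 20. These figures do not bear on the point, except that the 10% allowance corresponds to 2 men of 20.

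**Bounding the effect**

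Inputs: N = 20 and k = 2 (Section 13.1.2). Assumed, because the documents give no value: 1-year ADT-free survival S_r of 50% to 70% in retained men, all removed men censored before any event, and retained men followed to 1 year.

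- Kaplan-Meier estimate = S_r.
- Rate in all enrolled men = [(N − k) × S_r + k × S_k] / N, where S_k is the rate in removed men.
- Error = S_r − that rate = (k / N) × (S_r − S_k).

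Taking S_k to its limits with k = 2:

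- S_k = 0, S_r = 0.70: (18 × 0.70 + 0) / 20 = 0.63, error +7 points.
- S_k = 0, S_r = 0.50: 9 / 20 = 0.45, error +5 points.
- S_k = 1, S_r = 0.70: (12.6 + 2) / 20 = 0.73, error −3 points.
- S_k = 1, S_r = 0.50: (9 + 2) / 20 = 0.55, error −5 points.
- S_k = S_r: error 0.

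| Men removed early | If all have the event by 1 year | If none does |
|---|---|---|
| 1 of 20 | +2.5 to +3.5 points | −1.5 to −2.5 points |
| 2 of 20 | +5 to +7 points | −3 to −5 points |
| 4 of 20 (twice the allowance) | +10 to +14 points | −6 to −10 points |

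For scale, the standard error √[S(1 − S) / 20] is 11.2 points at S = 0.50, 11.0 at 0.60 and 10.2 at 0.70.

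**The case against.** The strongest reply is that the protocol never says follow-up stops at that point. The first sentence of 5.6 has no exception, and the second can be read as an extra safety duty. The calendar expects data from men who stop early, and Section 11.4.1 wants an ADT date for everyone. This stands as far as it goes: a reader might infer that the plan definitely follows these men only until the adverse event settles, but the restriction is an inference and several passages point against it. It does not remove the problem. Survival status alone supplies neither progression nor ADT start, and staff following Section 6 literally would end follow-up.

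The group is also narrow. The Section 6 sentence covers only men who cannot tolerate the reduced dose level, so extending it to everyone who stops for toxicity goes beyond the text. Section 13.1.2 allows 10% dropout and reports none in the Phase 1 study. A scenario with more than 2 of 20 removed therefore exceeds the plan's own allowance.

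Finally, a reader might infer that the estimates will look too favourable. Nothing in the documents links HCQ intolerance to prognosis, and the bounds run both ways. That objection stands in full.

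**Conclusion.** The text is inconsistent on whether men who cannot tolerate HCQ remain in outcome follow-up. On its natural reading, Section 6 with 5.6 censors them early for a treatment-related reason. That the censoring is informative is a risk, not something the documents can show, and its direction is unknown.

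The size stated above for 2 of 20 rests on the assumed 50% to 70% and on extreme outcomes in the removed men. At those extremes it is smaller than the standard error. Unlike sampling error, though, it would be a systematic shift, and it is avoidable. PFS and ADT-free survival are secondary estimates without a planned hypothesis test or comparator, and the primary PAR-4 test is not affected by this route. This is an inexpensive correction worth making, not a flaw that undermines the trial.

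**What to change.** Reconcile Sections 5.6, 6, 10 (calendar and note 3) and 11.4.1 so that the end of HCQ and the end of outcome follow-up are separate events. State that men who stop HCQ for toxicity still have progression, ADT start, QoL and survival collected at the planned timepoints, up to 3 years, unless consent is withdrawn.

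In 11.4 and 13.3.2, state that these men are included in the PFS and ADT-free survival analyses, and give a censoring rule for PFS. This should also make clear that the rule in 13.3 requiring 80% of planned HCQ does not exclude them from these two analyses, since it sits under a heading that covers secondary endpoints.

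No change to any dose or to any rule for stopping HCQ is proposed. The cost is a wording amendment and a small amount of continued follow-up and data collection for a few men.
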